prevalent case if they had a relevant record observed in the prior 1,825 days. In sensitivity analyses, 2-year partial prevalence will be estimated (using records in the prior 730 days) as will complete prevalence. For the latter, individuals will continue to be considered as a prevalent case from their first observed diagnosis or observation of chronic lymphocytic leukaemia up until the end of their observation time.

Acute myeloid leukaemia

Acute myeloid leukemia is the most common acute leukemia in older patients. Characterised by the infiltration of blood, bone marrow and sometimes other tissues by proliferative, poorly differentiated hematopoietic cells. Mostly presenting with nonspecific symptoms that begin gradually, or abruptly, and are the consequence of anemia, leukocytosis, leukopenia/leukocyte dysfunction, or thrombocytopenia, typically up to 3 months before diagnosis. Long-term survival is infrequent, at about 1 in 4 in 5 years from diagnosis.

For this study, cases will be identified based on a record indicating a diagnosis or observation of acute myeloid leukaemia. A clinical description along with a preliminary code list is provided in Appendix 1. For the primary analysis, 5-year partial prevalence will be estimated and so individuals will be considered as a prevalent case if they had a relevant record observed in the prior 1,825 days. In sensitivity analyses, 2-year partial prevalence will be estimated (using records in the prior 730 days) as will complete prevalence. For the latter, individuals will continue to be considered as a prevalent case from their first observed diagnosis or observation of acute myeloid leukaemia up until the end of their observation time.

Acute lymphocytic leukaemia

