Acute lymphocytic leukaemia is a type of cancer that affects white blood cells. In acute lymphocytic leukaemia, the process of development of blood cells is faulted, with immature, non-functioning leukemic cells being released from hematopoietic progenitors in the bone marrow or lymphatic system. This leads to anaemia, granulocytopenia, and thrombocytopenia, and causes symptoms of fatigue, weakness, breathlessness, infection, and haemorrhage. Common symptoms when patients first seek medical advice include fatigue and feeling breathless, repeated infections over a short time and unusual and frequent bleeding. Other symptoms can comprise pale, easily bruised skin; high temperature and night sweats; bone and joint pain as well as swollen lymph nodes, abdominal pain and unintentional weight loss. In some cases the central nervous system is also affected, with neurological symptoms including headaches, seizures, blurred vision or dizziness being reported. Acute lymphocytic leukaemia generally progresses quickly and aggressively, with immediate treatment being required. Prognosis is highly age-related, with cure rates of around 90% in children, decreasing to <10% in elderly or frail patients

For this study, cases will be identified based on a record indicating a diagnosis or observation of acute lymphocytic leukaemia. A clinical description along with a preliminary code list is provided in Appendix 1. For the primary analysis, 5-year partial prevalence will be estimated and so individuals will be considered as a prevalent case if they had a relevant record observed in the prior 1,825 days. In sensitivity analyses, 2-year partial prevalence will be estimated (using records in the prior 730 days) as will complete prevalence. For the latter, individuals will continue to be considered as a prevalent case from their first observed diagnosis or observation of acute lymphocytic leukaemia up until the end of their observation time.

	D2.2.3 – Study Protocol for C1-001	
	Author(s): [name], [name], [name], [name]	Version: 2.0 - Final
	Dissemination level: Public	

Table 4. Operational definition of the different outcomes

Outcome name	Details	Primary outcome?	Type of outcome	Wash out window	Care Settings ¹	Code Type ²	Diagnosis Position ³	Applied to study populations:	Measurement characteristics/ validation	Source of algorithm

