442095	Leukemic reticuloendotheliosis of intrathoracic lymph nodes

Observation domain

concept_id	concept_name
4180093	Chronic lymphocytic leukemia
46270567	History of chronic lymphocytic leukemia
37312112	Monoclonal B-cell lymphocytosis chronic lymphocytic leukemia-type
37312109	Monoclonal B-cell lymphocytosis non-chronic lymphocytic leukemia type
4186899	Chronic lymphoid leukemia - category

	D2.2.3 – Study Protocol for C1-001	
	Author(s): [name], [name], [name], [name]	Version: 2.0 - Final
		Dissemination level: Public

Acute myeloid leukaemia

Clinical description

Overview

Acute myeloid leukemia (AML) is the most common acute leukemia in older patients (median 65-70 y at diagnosis). Characterized by the infiltration of blood, bone marrow and sometimes other tissues by proliferative, poorly differentiated hematopoietic cells.

Presentation

Mostly presenting with nonspecific symptoms that begin gradually, or abruptly, and are the consequence of anemia, leukocytosis, leukopenia/leukocyte dysfunction, or thrombocytopenia, typically in the up to 3 months before diagnosis. Frequent symptoms include fatigue, fever, bleeding/haemorrhage, bruising, bone pain, cough, headache, excessive sweating/diaphoresis.

Physical examination could find signs of infection, retinal haemorrhage / papilledema, gum hypertrophy, splenomegaly, hepatomegaly, or lymphadenopathy. Thrombosis (stroke, MI, venous) or disseminated intravascular coagulation (DIC) can occur.

Blood tests could identify anaemia, leukocytosis or thrombocytopenia.

AML includes many subtypes, which we need to bear in mind for phenotyping purposes. This is the WHO 2016 classification for subtypes of AML:

Acute myeloid leukemia (AML) with recurrent genetic abnormalities

- AML with t(8;21)(q22;q22); RUNX1RUNX1T1
- AML with inv(16)(p13.1q22) or t(16;16)(p13.1;q22); CBFMBYH11
Acute promyelocytic leukemia with P M LR
- A R A
- AML with t(9;11)(p21.3;q23.3); MLLT3KMT2A
- AML with t(6;9)(p23;q34.1); DEKNUP214
- AML with inv(3)(q21.3q26.2) or t(3;3)(q21.3;q26.2); GATA2, MECOM
- AML (megakaryoblastic) with t(1;22)(p13.3;q13.3); RBM15MKL1
- Provisional entity: AML with BCABL1
- AML with mutated NPM1
- AML with biallelic mutations of CEBPA
- Provisional entity: AML with mutated RUNX1
AML with myelodysplasia related changes
- Therapy related myeloid neoplasms
AML, not otherwise specified (NOS)
- AML with minimal differentiation
- AML without maturation
- AML with maturation

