40483761	Acute myeloid leukemia with myelodysplasia-related changes
764781	Acute myeloid leukemia, minimal differentiation, FAB M0 in remission
764782	Acute myeloid leukemia without maturation, FAB M1 in remission
45765495	Core binding factor acute myeloid leukemia
45766268	Cytogenetically normal acute myeloid leukemia
36715587	Acute myeloid leukemia due to recurrent genetic abnormality
36717461	Therapy related acute myeloid leukemia and myelodysplastic syndrome
37110870	Acute myeloid leukemia with t(8;16)(p11;p13) translocation
37116722	Acute myeloid leukemia with t(6;9)(p23;q34) translocation
42539431	Acute myeloid leukemia with FMS-like tyrosine kinase-3 mutation
42538579	Therapy related acute myeloid leukemia due to and following administration of antineoplastic agent
35622003	Acute myeloid leukemia with NPM1 somatic mutation
35607963	Megakaryoblastic acute myeloid leukemia with t(1;22)(p13;q13)
35622696	Acute myeloid leukemia with CEBPA somatic mutations
35622760	Inherited acute myeloid leukemia
35623630	Acute myeloid leukemia and myelodysplastic syndrome related to alkylating agent
35623631	Acute myeloid leukemia and myelodysplastic syndrome related to topoisomerase type 2 inhibitor
35623633	Acute myeloid leukemia and myelodysplastic syndrome related to radiation
36683269	Acute myeloid leukemia with inv(3)(q21q26.2) or t(3;3)(q21;q26.2); RPN1-EVI1
3654662	Acute myeloid leukemia with inv(16)(p13.1q22) or t(16;16)(p13.1;q22) CFBF-MYH11
135762	Acute myeloid leukemia in remission
140352	Acute myeloid leukemia, disease
4326339	Smoldering chronic lymphocytic leukemia
4002497	Acute promyelocytic leukemia, FAB M3
4112803	Acute promyelocytic leukemia - hypogranular variant
4137687	Acute promyelocytic leukemia, FAB M3, in remission
36676614	Differentiation syndrome due to and following chemotherapy co-occurrent with acute promyelocytic leukemia
4175688	Hypergranular promyelocytic leukemia
4116880	Acute myelomonocytic leukemia - eosinophilic variant
44784490	Acute monoblastic leukemia in remission
140672	Acute monocytic leukemia in remission
4142105	Acute myelomonocytic leukemia, FAB M4, in remission
136930	Megakaryocytic leukemia in remission

	D2.2.3 – Study Protocol for C1-001	
	Author(s): [name], [name], [name], [name]	Version: 2.0 - Final
	Dissemination level: Public	

4139358	Erythroleukemia, FAB M6 in remission
4079686	Acute megakaryoblastic leukemia
138099	Erythroleukemia, FAB M6
4144191	Basophilic leukemia

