4003187	Acute myelomonocytic leukemia, FAB M4
135768	Acute monocytic leukemia
4003184	Acute panmyelosis with myelofibrosis
4082485	Acute monoblastic leukemia
4189938	Acute monocytic/monoblastic leukemia
4173970	Acute eosinophilic leukemia
132850	Myeloid leukemia in remission

Observation domain

concept_id	concept_name
4304355	Acute myeloid leukemia with abnormal marrow eosinophils
4304199	Acute myeloid leukemia, minimal differentiation
4304356	Acute myeloid leukemia without maturation
4304051	Acute myeloid leukemia with maturation
4029177	Acute myeloid leukemia with myelodysplasia-related changes
4028713	Acute myeloid leukemia, t(8;21) (q22;q22)
4029663	Acute myeloid leukemia, 11q23 abnormalities
4030263	Therapy-related acute myeloid leukemia and myelodysplastic syndrome
4031360	Acute myeloid leukemia, M6 type
4073533	Acute myeloid leukemia, no ICD-O subtype
4265011	Acute myeloid leukemia with recurrent genetic abnormality
4264447	Acute myeloid leukemia with multilineage dysplasia following a myelodysplastic syndrome or myelodysplastic syndrome/myeloproliferative disorder
4288090	Acute myeloid leukemia with multilineage dysplasia without antecedent myelodysplastic syndrome
4287472	Therapy-related acute myeloid leukemia and myelodysplastic syndrome, alkylating agent-related type
4265012	Therapy-related acute myeloid leukemia and myelodysplastic syndrome, topoisomerase type II inhibitor-related type
4184848	Acute myeloid leukemia
42872921	Mixed phenotype acute leukemia B/myeloid
42872922	Mixed phenotype acute leukemia T/myeloid
42872933	Acute myeloid leukemia with t(6;9)(p23;q34); DEK-NUP214
42872934	Acute myeloid leukemia with inv(3)(q21q26.2) or t(3;3)(q21;q26.2); RPN1-EVI1
42872942	Acute myeloid leukemia (megakaryoblastic) with t(1;22)(p13;q13); RBM15-MKL1
45771384	Acute myeloid leukemia with mutation of CEBPA (CCAAT enhancer binding protein alpha) gene
45766616	Acute myeloid leukemia with mutated NPM1

	D2.2.3 – Study Protocol for C1-001	
	Author(s): [name], [name], [name], [name]	Version: 2.0 - Final
	Dissemination level: Public	

37110871	Acute myeloid leukemia with t(8;16)(p11;p13) translocation
42535969	Acute myeloid leukemia with FMS-like tyrosine kinase-3 mutation
37204375	Acute myeloid leukemia with BCR-ABL1
37204557	Acute myeloid leukemia with mutated RUNX1
37312067	Acute myeloid leukemia with biallelic mutation of CEBPA (CCAAT enhancer binding protein alpha) gene
46273391	History of acute myeloid leukemia

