- Immunological assays for classification into B-cell lineage or T-cell lineage ALL leukaemias. B-Cell Lineage ALL: 70% of adult ALLs are of B-cell origin, T-Cell Lineage ALL: ~25% of adult ALLs are of T-cell

	D2.2.3 – Study Protocol for C1-001	
	Author(s): [name], [name], [name], [name]	Version: 2.0 - Final
	Dissemination level: Public	

lineage, Biphenotypic or Mixed Leukaemia, which express markers of both lymphoid and myeloid lineages on the same leukemic cells

- Cytogenetic and molecular analyses to define ALL subtypes, typically via standard cytogenetics, fluorescence in situ hybridization, and reverse transcriptase polymerase chain reaction.

Plan

- Pre-phase therapy: glucocorticoids (alone or combination) for ~5–7 days
- Induction therapy: typically vincristine, glucocorticoids, anthracyclines with or without cyclophosphamide or cytarabine. Adult ALL: L-Asparaginase is the only ALL-specific drug, targeted therapies including Tyrosine-kinase inhibitors (TKI, e.g. imatinib, dasatinib, nilotinib, ponatinib) for Ph+ ALL, immunological therapies (e.g. rituximab, blinatumomab)
- Post-remission consolidation: six to eight courses of high-dose methotrexate and/or cytarabine
- Maintenance treatment: 6-mercaptopurine and methotrexate plus intrathecal therapy, typically for 2–2.5 years. For Ph+ ALL maintenance includes TKI
- Stem Cell Transplantation is an essential part of the treatment strategy for adult ALL for high-risk patients.

Prognosis

Highly age-related, with cure rates of ~90% in children, decreasing to <10% in elderly or frail patients

MedDRA PTs

N/A

Disqualifiers

N/A

Strengtheners

- Minimal residual disease (MRD) during therapy
- Stem cell transplantation
- Diagnosis in young children
- previous chemotherapy, genetic disorders e. g. Down Syndrome, weakened immune system (HIV, AIDS)

Preliminary code list

Condition domain

concept_id	concept_name
36712834	Acute lymphoid leukemia relapse
36712835	Refractory acute lymphoid leukemia
136656	Subacute lymphoid leukemia
4139054	Subacute lymphoid leukemia in remission
37018868	Disorder of central nervous system co-occurrent and due to acute lymphoid leukemia in remission
37018869	Disorder of central nervous system co-occurrent and due to acute lymphoid leukemia
141816	Acute lymphoid leukemia in remission
134305	Acute lymphoid leukemia

	D2.2.3 – Study Protocol for C1-001	
	Author(s): [name], [name], [name], [name]	Version: 2.0 - Final

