	Dissemination level: Public	

4173963	B-cell acute lymphoblastic leukemia
4082461	Precursor B-cell acute lymphoblastic leukemia
4079280	Common acute lymphoblastic leukemia
4079281	Null cell acute lymphoblastic leukemia
4082462	T-cell acute lymphoblastic leukemia
4153344	Acute lymphoblastic leukemia, transitional pre-B-cell
4299143	Leukemic infiltration of skin (T-cell lymphoblastic leukemia)
4221907	Precursor T cell lymphoblastic leukemia/lymphoblastic lymphoma
4138008	Philadelphia chromosome-positive acute lymphoblastic leukemia
4138752	Precursor B-cell acute lymphoblastic leukemia in remission
4143997	T-cell acute lymphoblastic leukemia in remission
37017893	Philadelphia chromosome-negative precursor B-cell acute lymphoblastic leukemia
37109936	B lymphoblastic leukemia lymphoma with t(9;22) (q34;q11.2); BCR-ABL 1
3654647	B lymphoblastic leukemia lymphoma with t(5;14)(q31;q32); IL3-IGH
3654648	B lymphoblastic leukemia lymphoma with t(v;11q23); MLL rearranged
3654649	B lymphoblastic leukemia lymphoma with t(12;21) (p13;q22); TEL/AML1 (ETV6-RUNX1)
3654650	B lymphoblastic leukemia lymphoma with t(1;19)(Q23;P13.3); E2A-PBX1 (TCF3/PBX1)
3654651	B lymphoblastic leukemia lymphoma with hypodiploidy
3654653	B lymphoblastic leukemia lymphoma with hyperdiploidy
4003188	Adult T-cell leukemia/lymphoma
4081867	Acute biphenotypic leukemia
4227963	Precursor T-cell lymphoblastic lymphoma
134596	Lymphoid leukemia in remission

Observation domain

concept_id	concept_name
4030260	Precursor cell lymphoblastic leukemia
4029662	Precursor B-cell lymphoblastic leukemia
4030261	Precursor T-cell lymphoblastic leukemia
4264448	Precursor B-lymphoblastic leukemia/lymphoblastic lymphoma
4288091	Precursor T cell lymphoblastic leukemia/lymphoblastic lymphoma
4189936	Acute lymphoblastic leukemia - category
4143821	Philadelphia chromosome-positive acute lymphoblastic leukemia
42872925	B lymphoblastic leukemia / lymphoma - category
42872954	B lymphoblastic leukemia lymphoma, no ICD-O subtype
42872955	B lymphoblastic leukemia lymphoma with t(9;22)(q34;q11.2); BCR-ABL1
42872956	B lymphoblastic leukemia lymphoma with t(v;11q23); MLL rearranged
42872957	B lymphoblastic leukemia lymphoma with t(12;21)(p13;q22); TEL-AML1 (ETV6-RUNX1)
42872958	B lymphoblastic leukemia lymphoma with hyperdiploidy
42872959	B lymphoblastic leukemia lymphoma with hypodiploidy (Hypodiploid ALL)

	D2.2.3 – Study Protocol for C1-001	
	Author(s): [name], [name], [name], [name]	Version: 2.0 - Final

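### Mixed-lineage acute leukaemia counts as ALL when recorded as a Condition and as AML when recorded as an Observation

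*Protocol*

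**What the plan says.** Protocol section 8.6.2 uses one form of case rule for both acute leukaemias. For AML, "cases will be identified based on a record indicating a diagnosis or observation of acute myeloid leukaemia". For ALL, "cases will be identified based on a record indicating a diagnosis or observation of acute lymphocytic leukaemia". A Condition record and an Observation record therefore carry the same weight, and the two domain lists in Appendix I together define each outcome.

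For leukaemia of mixed lineage, Appendix I contains the following:

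- **AML, Observation domain:** "Mixed phenotype acute leukemia B/myeloid" (42872921) and "Mixed phenotype acute leukemia T/myeloid" (42872922).
- **ALL, Condition domain:** "Acute biphenotypic leukemia" (4081867).
- **ALL clinical description, Assessment:** in the item on lineage classification, after the B-cell and T-cell groups, "Biphenotypic or Mixed Leukaemia, which express markers of both lymphoid and myeloid lineages on the same leukemic cells".
- **AML clinical description, Presentation:** the WHO 2016 subtype list, which has no mixed or biphenotypic entry.

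The lists are headed as preliminary. Section 10 plans a systematic code search, relevance review by two clinical epidemiologists, and a run of CohortDiagnostics.

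**The concern.** A case definition should send the same disease to the same outcome whichever domain holds the record. Here it does not. Two patients with the same mixed-lineage leukaemia fall under different objectives if one has a Condition record and the other an Observation record. No rule makes the outcomes mutually exclusive, so a patient with both records is a case under Objective 5 and Objective 6. The protocol plans no sum over the six cancers, so this inflates no total, but it leaves the content of both estimates undefined for this group.

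Section 8.9 presents results separately by database. If source coding reaches different domains in different databases, a small part of any AML or ALL difference between them would reflect mapping rather than disease. The documents do not say whether the mapping differs in this way. The analyses in Table 5 vary prevalence type, point or period estimate, prior history and observable time. None varies the code scope, so none would reveal the problem.

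**Working it through.** **1. Which list holds the entity.** Counting rows by name in the four acute leukaemia lists of Appendix I:

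| Term | AML Condition (55 rows) | AML Observation (29) | ALL Condition (31) | ALL Observation (20) |
|---|---|---|---|---|
| Mixed phenotype | 0 | 2 | 0 | 0 |
| Biphenotypic | 0 | 0 | 1 | 0 |

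Each name occurs in one list only, and the two lists differ in both cancer and domain.

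**2. Whether the protocol regards them as one entity.** The ALL description joins biphenotypic and mixed leukaemia in a single item and defines it by lymphoid and myeloid markers on the same cells. The B/myeloid and T/myeloid names fit that definition. The item stands in the ALL classification and has no counterpart among the AML subtypes.

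**3. Consequence under section 8.6.2, for a patient with no other listed code.**

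- Condition record only: ALL case.
- Observation record only: AML case.
- Both records: a case of each.

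**4. Upper bound on the size.** The protocol gives no share for mixed leukaemia and no counts by code, so only a ceiling can be formed.

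- Inputs from the ALL description: 70% of adult ALL is B-lineage, about 25% is T-lineage, and adult incidence is 0.7 to 1.8 per 100,000 per year.
- Remainder: 100% − 70% − 25% = about 5%. Treating all of it as mixed is an inference from an approximate figure.
- Five-year partial prevalence with constant incidence and no deaths: 5 × 0.7 = 3.5 and 5 × 1.8 = 9.0 per 100,000, that is 0.35 to 0.90 per 10,000.
- Mixed part: 0.05 × 0.35 = 0.0175 and 0.05 × 0.90 = 0.045 per 10,000.
- Against the orphan threshold of 5 per 10,000 in section 6: 0.0175 / 5 = 0.35% and 0.045 / 5 = 0.9% of the threshold.
- In people, using the active subjects in Table 2: IPCI, 1.4 million × 0.0175 to 0.045 per 10,000 = about 2 to 6; SIDIAP, 5.8 million × the same = about 10 to 26.

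The head counts apply an adult rate to active subjects of all ages and assume that every such patient has an Observation record and no other ALL code. They show an order of magnitude only. The relative effect on AML cannot be computed, because the protocol gives no AML incidence.

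**The case against.** The lists are drafts, and section 10 plans a check of them: a systematic search, two clinical reviewers, and a tool meant to show how codes are used across databases and which were left out by mistake. That is a fair answer to omissions. It does not settle this case. The three codes are not omitted. Each can look relevant on its own list, and nothing in section 10 says which outcome owns an entity that sits under two.

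Broad codes also soften the effect. General AML and general ALL codes are listed in both domains, so a mixed-lineage patient who also carries a general ALL code is still counted as ALL. This stands, and it is one reason why the figures above are a ceiling. Such a patient would still be added to AML by a mixed-phenotype Observation record.

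Assigning a leukaemia with markers of both lineages to ALL is also a classification choice. This stands too. The point asks for consistency with the protocol's own description, and leaving the entity out of both outcomes would be equally consistent across domains.

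A reader might infer a wider defect in the AML lists. Appendix I says "AML includes many subtypes, which we need to bear in mind for phenotyping purposes", and the Condition list has rows such as "Acute promyelocytic leukemia, FAB M3" (5 promyelocytic rows, and 8 monocytic, monoblastic or myelomonocytic rows), while the Observation list names none of these. It is tempting to conclude that patients with these subtypes are lost when recorded as Observations. The documents do not support that. They do not show that Observation concepts exist for these subtypes, so the shorter list may only reflect what that domain holds. The AML Observation list also contains a general AML code (4184848) and a code for AML with recurrent genetic abnormality (4265011), the group under which the protocol places promyelocytic leukaemia. No size for such a loss can be derived from the protocol.

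**Conclusion.** The inconsistency is real and can be read directly from Appendix I: three codes for what the protocol describes as one entity are split between AML and ALL by record domain. It misclassifies a few patients and allows some to count under both objectives. The severity is minor. The ceiling is about 0.02 to 0.045 per 10,000, resting on four assumptions: the remaining 5% is all mixed-lineage, incidence is constant, nobody dies within five years, and all these patients are recorded only through the Observation codes. Even then it is under 1% of the 5 in 10,000 threshold and cannot affect a conclusion about rarity. The finding does not extend to the other AML subtypes.

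**What to change.** Before the code lists are finalised, state in section 8.6.2 which outcome takes mixed-lineage acute leukaemia, and apply that rule in both domains of Appendix I. Either of two edits does this:

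- Move 42872921 and 42872922 from the AML Observation list to the ALL Observation list. This agrees with the ALL clinical description and with 4081867 already being on the ALL Condition list. AML falls slightly and ALL rises slightly.
- Delete all three rows, so that the entity counts under neither cancer on these codes. Both estimates fall slightly.

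Separately, the section 10 code review can check whether Observation concepts exist for the AML subtypes that Appendix I names. That is a check to make, not a correction of a demonstrated error.

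The cost is an edit of two or three rows and one sentence. No new data are needed, and the milestone table still gives the creation and execution of the analytical code as to be confirmed.
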